The study will use a cohort study design to assess the clinical and economic impact and implementation of the intervention in NSW and ACT. Pharmacies will be onboarded from June 2024 to September 2024. This is due to administrative processes associated with MedAdvisor program installation, and the numbers of pharmacies that can be onboarded will be batched over this time. The study will be completed when 22,857 consults are reached or on 28 February 2025, whichever occurs first.

The intervention is multicomponent including Pharmacist training and support, and a Pharmacist-patient consultation, using an IT program, applying clinical guidelines. Pharmacies and pharmacists must meet the criteria of an 'approved pharmacy' and an 'approved pharmacist' outlined in the NSW Health Authority (Appendix 1), or a licence in ACT, to participate.

The 'approved pharmacist' will follow clinical practice guidelines originally developed by Queensland Health (Appendix 2). These guidelines have been through a co-design process (part of a separate low-risk ethics submission approved by HREC – University of Newcastle - H-2023-0448) and their content validated by dermatologists, GPs and NSW Health. These guidelines include a process for the pharmacist to make clinical decisions, and refer to other health professionals, particularly general practitioners.

The 'approved pharmacist' must complete the:

- Australasian College of Pharmacy modules on dermatology conditions; or

- Pharmaceutical Society of Australia module on dermatology conditions; and
- Modules developed by the University of Newcastle.

Pharmacists and pharmacies will be provided follow up support as part of a translational/ implementation strategy. Practice change facilitators will visit/contact these pharmacies during the study to provide ongoing support, answer any queries, ensure quality data is being collected, and collect implementation data. Pharmacies will be divided into low, medium and high contact, and this will depend on the number and nature of consultations delivered throughout the trial period.

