4.4 Participant (patient) recruitment

A flyer will be developed and approved by the NSW Ministry of Health to inform patients of the service and will be displayed in a prominent location in each participating pharmacy (Appendix 15). Patients will be opportunistically recruited in participating community pharmacies. Consecutive patients will be identified on presentation to the community pharmacy with symptoms suggestive one of the four skin conditions and either: presenting symptoms requesting advice or self-selecting a product for symptoms for the conditions included in this study - Impetigo, Atopic Dermatitis, Mild Plaque Psoriasis and Herpes Zoster. If meeting the below inclusion criteria, the pharmacist will make an offer to the individual to participate in the study. Patients will be asked for their informed consent to participate in the study via an electronic signature (Appendices 16-19).

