4.4.2 Participant (patient) inclusion criteria

The age requirements for participation vary depending on the condition:

- Mild to moderate atopic dermatitis, 6 months to 65 years old
- Herpes Zoster (Shingles), 18 years and older
- Impetigo, 12 month or above
- Mild plaque psoriasis, 18 years and older

If an individual meets the age requirements for their condition, the pharmacist may offer them participation in the trial and provide a consultation. This consultation could lead to (i) referral to a medical professional and/or (ii) an appropriate management and treatment plan, which may involve pharmacotherapy, supportive therapy, and general advice.

Specific referral criteria for each of the four skin conditions are outlined in the co-designed clinical guidelines for NSW/ACT in Appendix 2. These guidelines clearly define when and to whom timely referral should be made.

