4.6 Data sources

4.6.1 Community pharmacy data

During implementation of the intervention, information on health service delivery and program activities will be routinely captured in a case registration form by community pharmacists using the MedAdvisor application which is built into pharmacy software systems. For the purposes of evaluation and study participants will be assigned a unique study identification number, which will replace personal data sent to the trial team. The list of data that will be collected in these extracts is presented in Table 3.

Table 3: MedAdvisor data collection form included in the prescription software

Patient information	Type of field
Surname	Free text
First Name	Free text
Middle Name	Free text
Address	Free text
Suburb	Free text
Postcode	Free text
State	Drop down
Mobile	Free text
Phone number	Free text
Email	Free text
DOB	Date picker
Sex assigned at birth	Drop down
Gender	Drop down
Medicare number	Free text
Medicare expiry	Free text
DVA	Free text
Main language spoken at home	Free text
Aboriginal and/or Torres Strait Island Status	Drop down
Emergency contact Full name	Free text
Emergency contact Number	Free text
Pharmacist details	Type of field
Consultation date	Date picker
Pharmacist	Drop down
AHPRA number	Free text
Consent	Type of field
Please note age restrictions per service.... The age requirements for participation vary depending on the condition: - Mild to moderate atopic dermatitis, 6 months to 65 years old - Herpes Zoster (Shingles), 18 years and older - Impetigo, 12 month or above - Mild plaque psoriasis, 18 years and older	Text
Participants are required to provide e-consent using their mobile phone. If the patient does not have a mobile device, the pharmacy must provide a device to complete the consent.	Text

Patient has provided e-consent to participate. Consent pertains to this service and collection of their personal information.	Checkbox
Enter the e-consent validation code:	Numeric
Medical and social history	Type of field
Past medical history	Free text
Past surgical history	Free text
Medications from dispense	Table display per dispense record
Current medications	Free text
Allergies and known adverse medication reactions	Free text
Smoking history (including vaping)	Drop down
Alcohol history	Drop down
Standard drinks per day on typical drinking day	Numeric
Recreational drugs	Free text
Relevant family history	Free text
Relevant sexual activity	Free text
Relevant work, hobbies and other information	Free text

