4.9 Outcomes

Primary outcome

The primary outcome will be symptom resolution/relief (completely resolved, improvement, no improvement or worsening) (based on self-report at various time frames at follow up depending on the condition). This will be a composite measure based on patient self-reported data. As symptom resolution/relief time can be different for each of the four conditions, follow-up periods according to the clinical practice guidelines will be:

- 7 days for Impetigo, Psoriasis and Herpes Zoster (Shingles)
- 14 days for Atopic Dermatitis

Secondary outcomes

Secondary outcomes will be:

- Types of medication supplied for each condition by pharmacists. This is a participant specific outcome.
- Adherence rates to treatment protocol. This is a pharmacy-specific outcome.
- Numbers of patients supplied medications by pharmacists. This is a participant specific outcome.
- Numbers of patients provided self-care advice. This is a participant specific outcome.
- Numbers of patients referred to another health professional. This is a participant specific outcome.
- Reasons for patient referral to another health professional. This is a participant specific outcome.
- Estimated duration of consultation. This is a pharmacy specific outcome.
- Patient follow-up rate. This is a participant specific outcome.
- Patient adverse events. This is a participant specific outcome.
- Patient experience. This is a participant specific outcome.
- **Safety outcomes:** Patient-reported adverse events defined as any unfavourable and unintended sign, symptom or disease associated with the use of a medicine, which does not necessarily have to be caused by that medicine (Appendix 25).
- **Implementation outcomes**
 - Patient and provider program participation rates
 - Patient demographics (gender, DOB, education, employment status)
 - Numbers of patients per pharmacy assessed as eligible for pharmacy medication supply.
 - Numbers of patients supplied medication by pharmacists.
 - Estimated duration of consultation
 - Estimated time to complete all service requirements.
 - Adherence rates to treatment protocol
 - Prescriptions for first-line medications for the four skin conditions /Total medication prescriptions for the four skin conditions
 - Classification of appropriateness of medications for the four conditions as aligned with clinical practice guidelines.

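### The patient participation rate has no recorded denominator in the data sources described, and patient counts per pharmacy have no time base although pharmacies start up to 121 days apart

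*Protocol*

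**What the plan says.** Objective 1 (protocol section 3.2.2) covers reach, fidelity, adoption and variation in uptake between geographic regions. The implementation outcomes in section 4.9 that bear on it include "Patient and provider program participation rates", with neither numerator nor denominator defined, and two counts: "Numbers of patients per pharmacy assessed as eligible for pharmacy medication supply" and "Numbers of patients supplied medication by pharmacists". Section 4.10.4 plans descriptive statistics for all implementation outcomes.

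On timing, the synopsis (section 2) and section 3.2.1 state: "Pharmacies will be onboarded from June 2024 to September 2024". The reason given is the administration of software installation, and "the numbers of pharmacies that can be onboarded will be batched over this time". The study closes for everyone on 28 February 2025, or earlier if 22,857 consults are reached.

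On recruitment, section 4.4 has consecutive presenting patients identified, and for those who meet the criteria "the pharmacist will make an offer to the individual to participate in the study". Section 4.4.2 says that once the age requirement is met, "the pharmacist may offer them participation in the trial and provide a consultation". Section 4.6.1 gives Table 3 as the list of data in the pharmacy extract. Its consent item reads: "Patient has provided e-consent to participate. Consent pertains to this service and collection of their personal information".

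**The concern.** A patient participation rate needs the number of patients invited, or the number presenting. If only those who agree leave a record, the rate has a numerator and no denominator. A statistical analysis plan can choose a better estimator, but it cannot supply data that were never collected, so this has to be settled in the protocol and its forms. It also bears on comparison between jurisdictions. Under section 4.5.3 the NSW Government pays the $35 consultation fee, while ACT patients pay for the consultation themselves. Refusal could plausibly differ between the two, and the listed data would not show it.

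The count per pharmacy has a different weakness. With staggered starts and a common end, a pharmacy that joined in June has more time to accumulate patients than one that joined in September. A table of raw counts would show part of that difference as uptake.

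The two statements on offers add to the first problem. One describes an offer to every qualifying consecutive patient; the other can be read as leaving the offer to the pharmacist. Without a record of offers, nobody can tell which was followed.

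**Working it through.** The protocol states no figure for uptake or participation, so there is nothing to reproduce. The check has two parts.

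**1. Is there a patient denominator?** Each described source was checked for offers or refusals.

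- Table 3 (section 4.6.1): a checkbox for consent given and a validation code. There is no field for offer made, offer declined or reason. The items for no intervention and for a decision not to purchase are outcomes of a consultation that took place, not refusals of the service.
- Consent webform (section 4.4.1): described as a form that the participant completes, signs and submits. No record of refusal is described.
- Follow-up survey (section 4.6.2): goes only to people already in the trial.
- Facilitator contacts (section 4.6.3): roughly monthly, 10 to 20 minutes, open-ended, using the Appendix 21 checklist. Its contents are not shown.

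To show what is left undetermined, take the 22,857 consult ceiling as the number consenting (an illustration, treating each consult as one patient) and vary the share who accept. Offers = consenting / acceptance:

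| Assumed acceptance | Implied offers |
|---|---|
| 90% | 22,857 / 0.90 = 25,397 |
| 75% | 22,857 / 0.75 = 30,476 |
| 50% | 22,857 / 0.50 = 45,714 |
| 25% | 22,857 / 0.25 = 91,428 |

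The listed data look the same under all four rows.

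**2. How unequal is time on the service?** Active days = closing date minus start date. The protocol gives months only, so the first and last days of June and September are used as bounds.

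| Start | Days to 28 Feb 2025 |
|---|---|
| 1 June 2024 | 272 |
| 30 June 2024 | 243 |
| 1 September 2024 | 180 |
| 30 September 2024 | 151 |

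- Largest gap: 272 − 151 = 121 days; ratio 272 / 151 = 1.80. At the same daily rate the latest starter shows 1 − 151/272 = 44% fewer patients.
- Narrowest June–September contrast: 243 / 180 = 1.35.
- If the consult ceiling closed the study early (assumed dates), the largest ratio rises: 244 / 123 = 1.98 at 31 January 2025, and 213 / 92 = 2.32 at 31 December 2024.

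For regions, suppose that two have the same true rate, that all pharmacies start on either 1 June or 30 September, and that the early share differs (assumed values). The ratio of raw counts is the ratio of mean active days:

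| Early share, A vs B | Mean days, A vs B | Ratio |
|---|---|---|
| 50% vs 50% | 211.5 vs 211.5 | 1.00 |
| 60% vs 40% | 223.6 vs 199.4 | 1.12 |
| 80% vs 20% | 247.8 vs 175.2 | 1.41 |
| 100% vs 0% | 272 vs 151 | 1.80 |

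Divided by active time, every row gives 1.00.

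**The case against.** The strongest reply is that section 4.9 lists variables, not estimators. Dividing by active time is commonly left to the statistical analysis plan, and the inputs appear to exist: Table 3 records the consultation date, and under section 4.3 the research team itself triggers activation of the software. Descriptive statistics do not exclude rates. This stands in part. Nothing prevents a rate per active month, and the choice of regression model is properly left to the analysis plan. But the outcome as written is a count with no time base, and the protocol does not say that activation and end dates will be kept for this purpose.

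The reply on participation is that the Appendix 21 checklist might hold offer or refusal counts. That is possible and limits the claim accordingly, although a brief monthly discussion is a weak source for patient-level refusals. The provider half of the rate is not in question: section 4.3 has a list of invited pharmacies, which supplies a denominator.

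Three stronger readings might be inferred, and the documents do not support them.

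- *Regional results will be wrong.* Batching is attributed to software administration, with no stated link to region. The ACT licence step (section 4.3.1) makes a link conceivable but does not show one. With the same mix of start dates the ratio is 1.00.
- *Reach cannot be estimated at all.* Patient postcode is recorded, so reach can be expressed against area populations.
- *The primary outcome is biased by selective offering.* The difference in wording between sections 4.4 and 4.4.2 does not show that offers will be selective, and no direction or size can be derived. Recorded demographics, risk factors and condition allow some comparison of case mix between pharmacies.

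**Conclusion.** The point holds in two parts. The firmer one is that the patient participation rate cannot be estimated from the data sources the protocol describes, subject to what the unseen checklist contains. The second is that patient counts per pharmacy carry unequal exposure: a ratio of up to 1.80 between the earliest and latest possible starters, and at least 1.35 between any June and any September starter, assuming closure on 28 February 2025 and the same underlying rate. These ratios compare pharmacies. A distortion between regions follows only if start dates differ by region, and its size depends on how much. The two statements on offers need reconciling, but are a wording matter rather than evidence of selective recruitment. These changes should be made; they do not call the design into question.

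**What to change.** 1. Keep each pharmacy's activation and end dates. In section 4.9, state uptake as patients per active pharmacy-month, overall and by region, including activated pharmacies with no consultations. This costs almost nothing, since consultation dates are already collected and activation passes through the research team. The regression model, if any, can stay with the analysis plan.
2. Define numerator and denominator of the patient participation rate, and add a brief anonymous tally of offers made and declined before consent. The cost is a small change to the form and a little pharmacist time; some under-recording should be expected and reported. If Appendix 21 already collects these counts, say so in section 4.6. If a tally is not feasible, drop the patient rate and express reach against area population using recorded postcode, noting that this is a different quantity from acceptance of an offer.
3. Reconcile sections 4.4 and 4.4.2 so that a single rule states to whom an offer is made. This is an edit to the wording only.

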4.10 Data analysis

A mixed methods analytic approach will be applied.

4.10.1 Quantitative analysis

Descriptive statistics will be calculated for all study variables. Continuous variables will be reported using the appropriate measure of central tendency. Categorical variables will be summarized as proportions. Analyses will be conducted using SAS and R. The primary and secondary outcomes will be analysed with multivariable regression models adjusted for age). Sub-group analyses will be conducted to examine variation in outcomes for the cohort to assess a range of demographic and clinical characteristics.

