4.6.3 Implementation data

Practice change facilitators: The collection of the implementation data will be undertaken through visits/contacts (approximately monthly) within the resources available depending on the final number of community pharmacies participating, by practice change facilitators employed as part of the project. An open-ended discussion which, depending on the mode of contact, will vary between 10 to 20 minutes (see Appendix 21 for an implementation checklist to be used by practice change facilitators). Data will be collected using a pre-developed form in REDCap. Practice change facilitators will be trained by an implementation expert on models and frameworks of implementation science with an emphasis on the application of these to this specific study and the use of the checklist for data collection purposes.

Semi-structured interviews: A purposive list of stakeholders with in-depth knowledge about the constraints and enablers to successful implementation of the model will be identified using a snowballing method. We will ensure a diverse range of stakeholders are included - general practitioners, and people from professional bodies including the Pharmacy Guild, Pharmaceutical Society of Australia and the Royal Australian College of General Practitioners, and NSW Health administrators. Potential participants will be approached directly by a member of the study team at the University of Newcastle and asked if they are willing to be approached for interview. Names of those willing to be contacted will be provided to the research team at the George Institute, who will provide the potential interviewee with participant information sheets and follow the informed consent process as for the other groups of participants.

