4.10.3 Economic analysis

The analysis will be conducted from a health service perspective (base case) and a societal perspective including direct and indirect costs from the health-consumer's perspective - out of pocket expenses for any medicines or products provided, waiting time and travel time to attend treatment, productivity gains or time lost from work.

The scope of the within-study cost analysis is constrained by the design of the cohort study. Cost items associated with the co-design process, research and evaluation will be excluded. Resource use associated with the 2 components, pharmacy enrolment, training and support and pharmacy consultation, will be prospectively identified, measured and valued. In measuring resource use associated with delivery of the intervention, data will be collected from the research team, from the enrolled pharmacies and from the enrolled patients. Labour time will be measured using opportunity costs and valued based on Pharmacy Industry Award rates of pay, and average earnings for patients.

Results from the economic analysis will be expressed as (1) net benefit in terms of implementation costs and cost savings arising from more efficient treatment pathways; and (2) cost-consequence results accounting for patient experience measures, relevant safety outcomes and implementation measures.

[figure not shown]
Decision uncertainty will be accounted for using parametric and non-parametric bootstrapping to generate uncertainty intervals around the net benefit result.

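### The stated analysis, regression adjusted for age, makes no provision for the nesting of consultations in pharmacies; fitted as if consultations were independent, it would give intervals that are too narrow for overall rates and between-pharmacy contrasts

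*Protocol*

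**What the plan says.** Section 4.10.1 of the protocol names one model class and one adjustment: "The primary and secondary outcomes will be analysed with multivariable regression models adjusted for age". It adds subgroup analyses by demographic and clinical characteristics. It does not name a unit of analysis, a pharmacy or pharmacist term, or a method for standard errors.

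Other sections describe nested data:

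- Section 4.4: "Patients will be opportunistically recruited in participating community pharmacies".
- Section 4.9: "Adherence rates to treatment protocol. This is a pharmacy-specific outcome". Consultation duration carries the same label.
- Protocol Synopsis: "Pharmacies will be divided into low, medium and high contact, and this will depend on the number and nature of consultations delivered throughout the trial". Unequal volume between pharmacies is therefore expected.
- Protocol Synopsis, repeated in 3.2.1 and 4.5.3: "The study will be completed when 22,857 consults are reached or on 28 February 2025, whichever occurs first". Study size is counted in consultations.

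On economic uncertainty, section 4.10.3 says: "Decision uncertainty will be accounted for using parametric and non-parametric bootstrapping to generate uncertainty intervals around the net benefit result". The unit to be resampled is not given.

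**The concern.** One pharmacist, or a few, in each pharmacy assess, prescribe, refer and advise. Their habits, the local population and the level of facilitator support are shared by all patients of that pharmacy. Outcomes are therefore likely to be correlated within pharmacies, most of all those that record what the pharmacist did: prescribing, referral and adherence to the treatment protocol. Patient-reported symptom relief is probably less correlated.

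The protocol recognises a pharmacy level when it defines outcomes but gives it no place in the model. An analyst who follows 4.10.1 literally could treat up to 22,857 consultations as independent. Standard errors would then be too small in two places:

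- overall rates, which are the main product of a single-cohort study;
- contrasts between groups of pharmacies, such as region or NSW versus ACT, if these are modelled. Variation in uptake by region is part of objective 1, and the ACT contributes only 15 pharmacies.

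**Working it through.** **Figure in the plan.** The protocol gives 22,857 consultations as a maximum, without alpha, power, target rate, precision or ICC. There is no derivation to reproduce, so the number serves below only as the largest possible sample.

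**Inputs**

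- Maximum consultations: 22,857 (Protocol Synopsis).
- Number of pharmacies J: 15 in the ACT. The NSW number is not stated; section 4.6.3 says only "within the resources available depending on the final number of community pharmacies participating". Assumed 1,000 in total, with 500 and 1,500 as a range.
- Coefficient of variation (CV) of cluster size: not stated; assumed 1, with 0 for comparison.
- Survey response: not stated; assumed 40%.
- ICC: not stated; assumed 0.02 to 0.05 for the primary outcome and 0.05 for outcomes recorded at every consultation.

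**Formulas**

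- Mean cluster size: m = n / J
- Design effect: DE = 1 + (m(1 + CV²) − 1) × ICC
- Correct interval width relative to the independence interval: √DE
- True coverage of a nominal 95% independence interval: 2Φ(1.96/√DE) − 1

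**Primary outcome (survey), J = 1,000, CV = 1.** n = 0.4 × 22,857 = 9,143, so m = 9.14.

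- ICC 0.02: DE = 1 + (18.29 − 1) × 0.02 = 1.35; √DE = 1.16; coverage 90.9%.
- ICC 0.05: DE = 1 + (18.29 − 1) × 0.05 = 1.86; √DE = 1.37; coverage 84.9%.

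**Outcomes recorded at all consultations, J = 1,000, CV = 1.** m = 22.86.

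- ICC 0.05: DE = 1 + (45.71 − 1) × 0.05 = 3.24; √DE = 1.80; coverage 72.4%.

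**Sensitivity to the assumptions**

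| Outcome | J | CV | ICC | DE | Coverage |
|---|---|---|---|---|---|
| Survey | 500 | 1 | 0.02 / 0.05 | 1.71 / 2.78 | 86.6% / 76.0% |
| Survey | 1,500 | 1 | 0.02 / 0.05 | 1.22 / 1.56 | 92.4% / 88.4% |
| Survey | 1,000 | 0 | 0.02 / 0.05 | 1.16 / 1.41 | 93.1% / 90.2% |
| All consultations | 500 | 1 | 0.05 | 5.52 | 59.6% |
| All consultations | 1,500 | 1 | 0.05 | 2.47 | 78.7% |
| All consultations | 1,000 | 0 | 0.05 | 2.09 | 82.5% |

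With ICC = 0, DE = 1 and nothing changes.

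**Absolute size.** At an assumed rate of 80%, the independence half-width for 9,143 responses is 1.96 × √(0.8 × 0.2 / 9,143) = 0.82 percentage points. It becomes 0.82 × 1.37 = 1.12 points at ICC 0.05. For 22,857 consultations it goes from 0.52 to 0.52 × 1.80 = 0.93 points.

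**Repeat consultations.** With an assumed mean of 1.05 to 1.5 consultations per patient and within-patient correlation 0.3 to 0.6, DE = 1 + (r − 1) × ρ runs from 1.015 to 1.30. Intervals would need to be 1.01 to 1.14 times as wide, a small effect beside that of pharmacy.

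**The case against.** The strongest reply is that silence is not a decision. Multivariable regression does not exclude mixed models, GEE or robust standard errors, nothing in the protocol says consultations will be treated as independent, and a correlation structure is often left to the statistical analysis plan, which is not at hand. The sentence in 4.10.1 also ends in an unmatched bracket, so some wording may have been lost. This stands as far as it goes: the conclusion must be conditional. It does not remove the point, because the protocol does fix a model and an adjustment for every primary and secondary outcome and leaves out the main structural feature of its own data.

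Several stronger readings are tempting but not supported:

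- **All regression results will be too narrow.** Section 4.10.1 plans subgroups by demographic and clinical characteristics, which vary within a pharmacy. The design effect for an overall rate does not carry over to them. Regional variation in uptake is an implementation outcome, for which 4.10.4 plans descriptive statistics.
- **The economic intervals are wrong.** They come from a bootstrap, not from the age-adjusted model. Resampling whole pharmacies would handle the clustering.
- **Patients contribute several records.** The protocol neither describes nor excludes repeat consultations; it says only that "study participants will be assigned a unique study identification number".
- **A pharmacy-specific outcome cannot be regressed on patient age.** Consultation length is recorded per consultation, so a consultation-level model for duration or adherence is coherent once it allows for clustering.

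It is also fair to say that 22,857 is a ceiling. Fewer consultations over the same pharmacies would mean smaller clusters and a smaller design effect. The absolute change is around a percentage point or less, and the protocol states no comparator or target rate on which a decision would turn.

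**Conclusion.** The concern holds in conditional form. Section 4.10.1 does not provide for the pharmacy nesting that the protocol describes. If its model is fitted with consultations treated as independent, intervals for overall rates and for contrasts constant within a pharmacy would be too narrow whenever the ICC exceeds 0. Under the central assumptions, coverage is about 91% to 85% for the primary outcome and about 72% for outcomes recorded at every consultation. These figures illustrate scale and do not predict it: the number of pharmacies, cluster-size spread, response rate and ICC are all assumed. The bootstrap and repeat-consultation points are requests for clarification, not demonstrated errors. This should be fixed, with moderate confidence; it does not amount to a fatal flaw.

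**What to change.** 1. In 4.10.1, state that consultation-level outcomes, including adherence and duration, will be fitted with a pharmacy random effect, or with GEE or robust standard errors clustered on pharmacy. Align the pharmacy-specific labels in 4.9 with that unit of analysis.
2. State whether a patient may have more than one consultation. If so, use one index consultation per patient per condition for the primary outcome.
3. In 4.10.3, state that the non-parametric bootstrap resamples pharmacies.
4. If the statistical analysis plan already covers these points, bring the protocol wording into line with it.

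The cost is a few sentences. Pharmacy and participant identifiers already appear in the data flow (4.7.4 and 4.8); it should be confirmed that the consultation extract carries the pharmacy identifier. The only downside is wider intervals.
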